#### 4.6.2.4 Treatment success for surgery

The investigator's overall clinical assessment of hemostatic efficacy for surgical prophylaxis based on the 4-point ordinal efficacy evaluation (See Table 7 of Section 8.5.2.1 of the clinical protocol for details) for surgical treatment scale (excellent, good, moderate, poor/none) will be tabulated overall and by type of surgery (i.e., emergency surgeries, non-emergency surgeries). The treatment success rate, defined as the percentage of surgical hemostasis ratings of excellent or good, will be presented. . Missing assessments will be excluded from the analysis.

Surgical prophylaxis will be summarized for the Surgery population.

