5.5 Rescue Therapy

Other marketed FVIII products should be used as rescue medication only when there is poor / no hemostatic response to rVIII-SingleChain as defined in [Section 8.4.1](#) or when rVIII-SingleChain is not available (eg, emergency use).

The PUPs in Arm 2 using a FVIII product as rescue medication must be withdrawn from the study (see [Section 4.2.1](#)). The PTPs in Arms 1 and 3 using a FVIII product as rescue medication do not need to be withdrawn from the study.

The use of bypassing agents (ie, activated recombinant factor VII [rFVIIa] or activated prothrombin complex concentrate [aPCC] / factor eight inhibitor bypassing agent [FEIBA]) is permitted in subjects with inhibitors.

6 Allocation, Dosing and Administration

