8.5 Treatment for Surgery

Subjects undergoing surgery may be treated with rVIII-SingleChain (see [Section 3.2.4](#) and [Section 6.2.3](#) for surgery dose and surgery treatment). All subjects undergoing surgery may enroll in the surgery substudy. Subjects who enroll in the surgery substudy will return to the main study at the end of participation, as outlined in [Section 8.5.3](#). Doses of rVIII-SingleChain administered before and after surgery will be documented.

All invasive procedures other than surgery will not be included in the surgery substudy. Subjects undergoing an invasive procedure other than surgery may be treated with rVIII-SingleChain. However, invasive procedures other than surgery are considered medical events of special interest and should be documented in the eCRF.

If a subject has an emergency surgery and rVIII-SingleChain is not available, the subject may substitute rVIII-SingleChain with a marketed FVIII product during surgery; the surgery will

not be included in the surgery substudy. Subjects in **Arms 1 and 3 (PTPs)** may return to the study after the emergency surgery at the discretion of the investigator and sponsor. If a subject has a planned surgery and uses any FVIII product other than rVIII-SingleChain, the subject must be withdrawn from the study.

Subjects in **Arm 2 (PUPs)** must be withdrawn from the study if they receive any FVIII product other than rVIII-SingleChain, irrespective of the type of surgery (emergency or planned) for which that FVIII product was administered. Inhibitor positive patients who require surgery are not eligible for the surgery substudy, as the surgical procedure should be covered by bypassing agent.

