8.5.2 Surgery Substudy Assessments

8.5.2.1 Efficacy Assessment by Investigator for Surgery

The investigator will assess the efficacy of rVIII-SingleChain by using a 4-point surgical treatment rating scale of “excellent”, “good”, “moderate”, or “poor / no response” after the end of surgery and record results in the eCRF (see [Table 7](#)).

Table 7: Investigator assessment of hemostatic efficacy of rVIII-SingleChain for surgery substudy

Category	Description
Excellent	Hemostasis clinically not significantly different from normal (eg, achieved hemostasis comparable to that expected during similar surgery in a non-factor deficient patient) in the absence of other hemostatic intervention and estimated blood loss during surgery is not more than 20% higher than the predicted blood loss for the intended surgery.
Good	Normal or mildly abnormal hemostasis in terms of quantity and / or quality (eg, slight oozing, prolonged time to hemostasis with somewhat increased bleeding compared to a non-factor deficient patient in the absence of other hemostatic intervention) or estimated blood loss is greater than 20% but less than or equal to 30% higher than the predicted blood loss for intended surgery.
Moderate	Moderately abnormal hemostasis in terms of quantity and / or quality (eg, moderate hemorrhage that is difficult to control) with estimated blood loss greater than what is defined as Good.
Poor / No response	Severely abnormal hemostasis in terms of quantity and / or quality (eg, severe hemorrhage that is difficult to control) and / or additional hemostatic intervention required with another FVIII product, cryoprecipitate, or plasma for complete resolution.

Abbreviations: FVIII = coagulation factor VIII; rVIII-SingleChain = single chain recombinant factor VIII.

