#### Arm 2 (PUPs)

##### Treatment success for major bleeding episodes

The number of bleeds and the number of treated bleeds will be presented. The percentage of bleeds treated successfully will be reported with a 95% CI. To estimate this percentage, the numerator will include the number of bleeding episodes treated with rVIII-SingleChain and rated as "excellent" or "good" (See Table 6 in Section 8.4.1 of the clinical protocol for details); and the denominator will include all treated bleeding episodes. Missing assessment will be counted as failures. With this approach, the following treated bleeds will be considered treatment failures in the primary analysis: those with ratings of "moderate", or "poor/none"; those treated with products other than rVIII-SingleChain regardless of the assessment; and those with missing investigator ratings. In order to account for within-subject correlation, generalized linear modeling using SAS' GENMOD procedure will be utilized. The model will contain only the intercept term. The binomial distribution with logit link function will be specified.

Two sensitivity analyses of the primary endpoint will be performed:

- In the first sensitivity analysis, missing investigator ratings will be excluded from the denominator.
- In the second sensitivity analysis, missing investigator ratings will be counted as treatment successes.

Results will be presented overall and by treatment modality.

Only bleeding episodes classified as major will be included in this analysis. Bleeding episodes reported by the subject in the eDiary will be excluded since major/minor classification is not collected.

Major and minor bleeds by inhibitor status will be summarized for PUPs.

CCI

Summary of rVIII-SingleChain treated bleeding events will be listed while inhibitor positive and per patient.

rVIII-SingleChain Non-Inhibitory Anti-Drug Antibodies, patient related risk factor, treatment related risk factor will be listed for PUPs.

Treatment related risk factor and patient related risk factor will be summarized by inhibitor group.

Bleeding events not treated with rVIII-SingleChain will be listed for PUPs.

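### Surgeries without a rating are dropped from the surgical success rate with no sensitivity analysis, whereas the bleed analysis counts missing ratings and use of other products as failures

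*SAP*

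**What the plan says.** **Surgery.** SAP 4.6.2.4 tabulates the investigator's 4-point rating and defines the summary: "The treatment success rate, defined as the percentage of surgical hemostasis ratings of excellent or good, will be presented". It then says "Missing assessments will be excluded from the analysis". No sensitivity analysis follows. SAP 4.12.2 rules out imputation beyond partial dates and the primary efficacy endpoint.

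For the scale, the SAP points to the protocol ("See Table 7 of Section 8.5.2.1 of the clinical protocol for details"). In that table the lowest category, Poor / No response, covers "additional hemostatic intervention required with another FVIII product, cryoprecipitate, or plasma for complete resolution". The top category applies only "in the absence of other hemostatic intervention and estimated blood loss during surgery is not more than 20% higher" than predicted.

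**Bleeds.** For major bleeds in Arm 2, SAP 4.6.1.1 says "Missing assessment will be counted as failures". It also treats bleeds managed with any other product as failures irrespective of the rating. Two sensitivity analyses follow: missing ratings excluded, and missing ratings counted as successes.

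**Withdrawal.** Protocol 8.5: "If a subject has a planned surgery and uses any FVIII product other than rVIII-SingleChain, the subject must be withdrawn from the study". Protocol 5.5: "The PTPs in Arms 1 and 3 using a FVIII product as rescue medication do not need to be withdrawn from the study". Protocol 7.2 lets rescue follow a poor response on the surgery scale as well as on the bleed scales. Previously untreated patients (PUPs) who receive another FVIII product must be withdrawn under Protocol 4.2.1, 5.5 and 8.5 alike.

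**The concern.** Both endpoints rest on a 4-point investigator rating with success defined as excellent or good, yet missing ratings are handled in opposite ways and no reason is given. Surgical success is a secondary endpoint in all arms, and the number of surgeries may be small, so one or two unrated cases can visibly move the percentage.

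The bleed analysis also has a safeguard that surgery lacks. The bleed scales (protocol Tables 5 and 6) already place use of another FVIII product in their lowest category, but the SAP still adds an analysis rule that overrides the recorded rating. Surgery relies on the scale wording alone.

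The withdrawal texts are a separate matter. For a PTP rescued with another FVIII product at a planned surgery, one section removes him from the study and another does not, so two sites could handle the same patient differently.

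**Working it through.** **1. Figures in the documents.** There are none to reproduce. SAP 3.9 sets no target number of subjects for the surgery substudy, and the plan gives no expected success rate or missing rate for this endpoint. All counts below are assumptions.

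**2. Direction of the effect.** Let N be the surgeries in the substudy, S those rated excellent or good, and m those unrated.

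- Plan (unrated excluded): S/(N − m)
- Bleed rule (unrated as failures): S/N
- Other bound (unrated as successes): (S + m)/N

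Since N − m ≤ N, the first rate is never below the second. The difference is S·m/[N(N − m)], which is zero when m = 0.

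**3. Illustrative size.** S is set at 90% of N. The intervals are Clopper-Pearson 95% intervals added here for scale; the SAP plans none for this endpoint.

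| N | S | m | Excluded (plan) | As failures | As successes | Rise, plan over failures |
|---|---|---|---|---|---|---|
| 10 | 9 | 1 | 9/9 = 100% (66.4 to 100) | 9/10 = 90.0% (55.5 to 99.7) | 10/10 = 100% | 10.0 points |
| 20 | 18 | 1 | 18/19 = 94.7% (74.0 to 99.9) | 18/20 = 90.0% (68.3 to 98.8) | 19/20 = 95.0% | 4.7 points |
| 20 | 18 | 2 | 18/18 = 100% (81.5 to 100) | 18/20 = 90.0% (68.3 to 98.8) | 20/20 = 100% | 10.0 points |
| 30 | 27 | 1 | 27/29 = 93.1% (77.2 to 99.2) | 27/30 = 90.0% (73.5 to 97.9) | 28/30 = 93.3% | 3.1 points |
| 30 | 27 | 3 | 27/27 = 100% (87.2 to 100) | 27/30 = 90.0% (73.5 to 97.9) | 30/30 = 100% | 10.0 points |

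A larger unrated share gives a larger gap: with 2 unrated of 10 and the other 8 successful, 8/8 = 100% against 8/10 = 80%.

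**4. What Table 7 already settles.** A rescued surgery rated as Table 7 directs is Poor / No response. It stays in the denominator as a failure and causes no inflation. Three cases remain:

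- The surgery has no rating, so Table 7 cannot score it.
- The rating departs from Table 7. The Good row offers blood loss 20% to 30% above prediction as an alternative limb, with no condition on other intervention, so a surgery that needed another FVIII product could fit both Good and Poor.
- Another product was given but was not needed for complete resolution. Table 7's lowest row does not clearly cover this.

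**5. Withdrawal texts side by side, for a PTP at planned surgery with a poor response.**

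- Protocol 7.2 allows another FVIII product as rescue and cites the surgery scale.
- Protocol 5.5 says such rescue does not require withdrawal of a PTP.
- Protocol 8.5 requires withdrawal for any other FVIII product at planned surgery, with no exception for rescue.

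These cannot all be followed.

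**The case against.** The strongest case against has five parts.

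- **Another product is already scored.** A reader might infer that nothing in the plan scores use of another FVIII product at surgery. That is wrong: SAP 4.6.2.4 cites Table 7, which does. This stands, and it confines the gap to the cases in step 4.
- **Withdrawal does not remove a surgery.** A reader might also infer that patients withdrawn after rescue take their failed surgeries out of the rate. The documents do not support this. The Surgery population requires only one surgical dose of study product (SAP 3.5.4), and the investigator rates after surgery (Protocol 8.5.2.1). Protocol 4.2.2 asks for attempts at a final assessment on withdrawal. Nothing links withdrawal to a missing rating. It is fair to add that 4.2.2 puts its strongest requirement on safety assessments and that 8.5.2.1 sets no fixed time for the surgical rating. So the rating is not specifically secured, but that does not show it will be lost.
- **The comparison is with a primary endpoint.** The failure rule and sensitivity analyses are written for the Arm 2 primary endpoint. Surgery is secondary and descriptive, and exclusion is openly pre-specified. This lowers the weight of the point but does not explain why the count of unrated surgeries and the alternative result are not shown.
- **PTP work is finished.** Protocol 1.3 marks the PTP exposure target as completed. The SAP's change list records the PTP report as completed in November 2019, and SAP 4.1.2 says the PTP analysis was done before COVID-19. This stands.
- **A blanket rule could mis-score supply problems.** Protocol 8.5 keeps out of the substudy an emergency surgery covered by another product because study product was unavailable. Since the Surgery population is defined by subject, a loosely worded rule could pull such a surgery back in as a failure. This stands, and the fix is limited accordingly.

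**Conclusion.** The point holds in a limited form. For surgeries whose rating is missing, the stated rule can only raise the success rate or leave it unchanged relative to the bleed rule. With the assumed counts in the table the rise is about 3 to 10 points; it is zero if every surgery is rated. For surgeries whose recorded rating does not follow Table 7, the SAP has no override like the one for bleeds. The endpoint is descriptive, so no error rate or power is affected.

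The conflict between Protocol 5.5 and 7.2 on one side and 8.5 on the other is real. A reader might go further and conclude that it still threatens the PTP primary endpoint, because under Protocol 11.3.3.2 an inhibitor-free PTP withdrawn before 100 exposure days (EDs) is not in the denominator. With PTP follow-up and analysis complete, rewording can no longer change who reached 100 EDs. What remains is to report which rule was applied.

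**What to change.** In SAP 4.6.2.4, make the unit the surgery and restrict it to surgeries included in the surgery substudy. Emergency surgeries that Protocol 8.5 excludes because study product was unavailable stay out. Within that set:

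- count as not successful any surgery with a missing rating, and any surgery in which another FVIII product was used as rescue, regardless of the rating;
- show the result with missing ratings excluded as a sensitivity row;
- report the number of unrated surgeries.

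For PTPs, whose analysis is complete, present this as a labelled supplementary row and leave the reported result in place.

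Separately, reconcile Protocol 5.5 and 7.2 with 8.5 on withdrawal of a PTP given another FVIII product as rescue at planned surgery, and state in the report which rule was applied.

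The cost is a short SAP revision, one table row with a count, and a protocol clarification. The downside is that a surgery left unrated for administrative reasons counts against the product; the sensitivity row and the count let the reader see how much that matters.

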#### 4.6.3 Other Efficacy Endpoints

##### 4.6.3.1 Time between the last injection and the next bleeding episode

The time (in hours) between the last injection and the next bleeding episode will be derived. This will only be derived for bleeding episodes that occur during the efficacy evaluation period. For bleeding events with missing time, time to most recent infusion will be derived imputing time to 00:00. Negative values will be reported as zero. Times will be grouped into the following intervals:  $\leq 24$ ,  $>24$  to  $\leq 48$ ,  $>48$  to  $\leq 72$ ,  $>72$  to  $\leq 96$ ,  $>96$  hours after the preceding injection. These will be presented in the listings, which will include as a minimum the following information: type of subject, arm, modality, cause (spontaneous, traumatic, unknown), actual time in hours, and time category.

##### 4.6.3.2 Location of bleeding episodes

The characteristics of bleeding episodes including the type of event (traumatic or spontaneous or unknown causality) and the location of bleeding will be summarized using frequency counts and percentages. Tables will be provided separately for all bleeds, traumatic bleeds, spontaneous bleeds and bleeds with unknown causality.

#### 4.6.4 Other Analyses for the Surgical Substudy

The following information will be summarized using descriptive statistics, or presented qualitatively as appropriate:

- Predicted and estimated blood loss during surgery.
- Predicted and actual transfusion requirements during surgery.
- Change in hemoglobin levels between baseline, during surgery, and after surgery.

These data will be presented for the Surgery population.

Surgical, postoperative details, blood loss and transfusion requirements will be listed while inhibitor positive and for all subjects.

### 4.7 Safety Analysis

Safety data will be summarized using the Safety population, the Surgery population and the  population. Unless specify otherwise, safety data will be summarized separately for the PTPs (Arm 1 and Arm 3) and PUPs (Arm 2) and by age group for PTPs: 0 to < 6 years,  $\geq 6$  to < 12 years,  $\geq 12$  to < 18 years and  $\geq 18$  to  $\leq 65$  years, 0 to <12 years,  $\geq 12$  to  $\leq 65$  years.

#### 4.7.1 Incidence of Inhibitor Formation

The incidence of inhibitor formation to FVIII will be estimated for subjects in the Safety population who did not have inhibitors at baseline. Baseline assessments are defined as those assessments done before date and time or on the same date and time of the first dose. If time of inhibitors assessment or time of first dose is missing then the inhibitor result taken at the same date of the first dose will be considered as baseline. Inhibitor formation will be defined as any post-baseline inhibitor titer  $\geq 0.6$  BU/mL identified and confirmed by re-testing at a subsequent visit. Both tests must be performed by a central laboratory. A positive result not confirmed as positive by re-testing at a subsequent visit result will be considered as non positive. In the KM analysis of inhibitor occurrence, the first positive result will be considered as an event. A positive result not confirmed as positive by re-testing at a subsequent visit result will not be considered as an event. Positive FVIII inhibitors will be further categorized as low or high titer. Low-titer inhibitors are defined as positive inhibitors with a titer of  $\leq 5$  BU/mL. High-titer inhibitors are defined as positive inhibitors with a titer of  $> 5$  BU/mL.

For the inhibitor incidence after 10 Total EDs, the numerator will include all subjects with inhibitors observed at the closest visit up to 10 EDs ( $\leq 10$  EDs). The denominator will include all subjects with at least 10 EDs ( $\geq 10$  EDs) plus subjects with less than 10 EDs but with inhibitors.

- Numerators = Number of PTP subjects who develop inhibitors up to 10 EDs ( $\leq 10$  EDs)
- Denominators = Total number of PTPs with at least 10 EDs ( $\geq 10$  EDs) + subjects with less than 10 EDs with inhibitors. Subjects not tested at  $\leq 10$  EDs will be excluded.

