8.6 Blood Samples for Inhibitors, Antibodies, Incremental Recovery and FVIII Activity Level

If the investigator collects a blood sample for inhibitor assessment at any time during the study, the local laboratory results must be recorded in the eCRF and a duplicate sample must be submitted for analysis to the central laboratory. A positive inhibitor result (local or central) must be repeated and a duplicate submitted to the central laboratory as soon as possible after receiving the laboratory report to rule out laboratory errors.

If the investigator collects a blood sample for FVIII activity levels at any time during the study, a duplicate sample must be sent to the central laboratory.

CCI

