8.6.1 Blood Samples for Inhibitors and Antibodies

The presence of inhibitors to FVIII, antibodies against rVIII-SingleChain, and antibodies against CHO proteins will be analyzed by the central laboratory. For the inhibitor blood samples, subjects should have a 4-day washout from last FVIII infusion before blood draw if possible.

1. In **Arms 1 and 3 (PTPs)**, blood samples for inhibitors to FVIII, antibodies to rVIII-SingleChain, and antibodies to CHO proteins will be collected at the closest visits after 10 EDs, after 50 EDs, and after 100 EDs as outlined in [Table 8](#).
2. In **Arm 2 (PUPs)**, blood samples for inhibitors to FVIII, antibodies against rVIII-SingleChain, and antibodies to CHO proteins will be collected at all scheduled visits.

Blood samples drawn for inhibitor assessment should be sent to the central laboratory for testing with the Nijmegen assay. A subject will be considered to have developed an inhibitor if the titer result is ≥ 0.6 BU/mL and verified by repeat testing. FVIII inhibitors will be further categorized as low-titer (≤ 5 BU/mL) and high-titer (> 5 BU/mL). If an inhibitor is suspected, all inhibitor testing must be expedited and a repeat sample obtained as soon as possible to confirm results.

Details regarding sample collection, handling, deep freezing of samples and shipment to the central laboratory are given in the Laboratory Manual in the Investigator Site File.

If an inhibitor is suspected (eg, lack of efficacy of IMP), additional visits may be scheduled for inhibitor assessment. If a subject undergoes surgery, blood samples will be collected at least 28 days after surgery to test for inhibitors to FVIII, antibodies against rVIII-SingleChain, and antibodies against CHO proteins in all study arms. In addition, a pre-surgery blood sample for inhibitor testing is recommended for PUPs in Arm 2.

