8.10.6 End of Study

For subjects in all study arms, the End of Study Visit should take place at the end of the planned treatment period, ie:

- After at least 100 EDs in Arms 1 and 3 [PTPs].
- After 75 EDs if inhibitor negative.
- If inhibitor positive, after the 12-month post eradication follow up period or after 24 months of inhibitor treatment without CCI ().
- If the subject discontinues prematurely.
- If the sponsor terminates the study.

No further study-related procedures will be performed after the End of Study Visit, except for follow-up of ongoing AEs (see [Section 9.9](#)) and inhibitor SAEs in Arm 2 PUPs (see [Section 9.10](#)).

8.10.6.1 End of Study Visit for Arm 1

In **Arm 1**, the following procedures will be performed at the End of Study Visit:

- Obtain hemophilia A social history and activity level.
- Obtain blood sample for inhibitors to FVIII.
- Obtain virology retention sample.
- Review and collect of subject eDiary.
- Record investigator assessment for treatment efficacy of any treated bleeding episodes.
- Collect all vials (used, partially used, and unused) of rVIII-SingleChain.
- Assess drug accountability.
- Review AEs.
- Review concomitant medications.

8.10.6.2 End of Study Visit for Arms 2 and 3

In **Arms 2 and 3**, the following procedures will be performed at the End of Study Visit:

- Obtain hemophilia A social history and activity level.
- Obtain blood sample for serum chemistry and hematology.
- Vital signs.
- Physical examination.
- Record weight and height.
- Obtain blood sample for inhibitors to FVIII.
- Obtain blood sample for antibodies against rVIII-SingleChain and CHO proteins.
- Obtain virology retention sample.
- Review and collect of subject eDiary.
- Record investigator assessment for treatment efficacy of any treated bleeding episodes.
- Collect all vials (used, partially used, and unused) of rVIII-SingleChain.
- Perform drug accountability.
- Review AEs.
- Review concomitant medications.

9 Adverse Events

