### 3.5.6 Subgroups/Subpopulations

The following subgroups will be defined:

- Age based on age in this study:
  - For PTPs (Arm 1 and Arm 3): 0 to < 6 years,  $\geq 6$  to < 12 years,  $\geq 12$  to < 18 years and  $\geq 18$  to  $\leq 65$  years, 0 to <12 years,  $\geq 12$  to  $\leq 65$  years;
- By Region (Europe, US, Rest of the world, Asia)
- Japan subgroup

Efficacy endpoint will be analyzed by

- Positive vs. negative test for non-inhibitory Anti-Drug Antibodies (ADAs) during the Study.

The incidence of inhibitors will be summarized by

- Race (White, Black, Asian, and Other)

Annualized Bleeding Rates will be presented by

- ADA status (Positive and Negative)

For PUPs analyses for Annualized Bleeding Rates, hemostatic efficacy, TEAE and IR will be presented by inhibitor status (Positive and Negative) at the time of assessment.

CCI

Analyses by inhibitor status or inhibitor group have been defined in this SAP within relevant sections, the definition of inhibitor status and inhibitor group are the following ones:

*Inhibitor positive*

A subject is inhibitor positive if he developed a titre value (from the central lab) of at least 0.6 BU/mL, and was also confirmed in the next assessment with a titre value of at least 0.6 BU/mL.

*Inhibitor negative*

[figure not shown]
A subject is inhibitor negative if his titre value (from the central lab) was below 0.6 BU/mL.

*Inhibitor eradicated*

It refers to a subject who was previously documented with a confirmed inhibitor positive titre result and at a later point in the study, his titre value decreased and became low enough to classify him as inhibitor negative (titre value < 0.6 BU/mL). However, in order to become inhibitor eradicated, an inhibitor positive subject must first present an initial inhibitor negative titre result which must be confirmed in the next assessment by another inhibitor negative titre result.

*Inhibitor status*

A subject's inhibitor status represents a period in the study in which he is either inhibitor positive (+) or inhibitor negative (-), depending on his titre value at a given time.

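### SAP 4.7.1 scores a positive inhibitor result that was never re-tested the same as one refuted by re-test, which can only lower the reported incidence

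*SAP*

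**What the plan says.** **SAP.** Section 4.7.1 counts a post-baseline titer of at least 0.6 BU/mL as inhibitor formation when a re-test at a later visit confirms it, and adds "Both tests must be performed by a central laboratory". It then says "A positive result not confirmed as positive by re-testing at a subsequent visit result will be considered as non positive" and, for the time-to-event analysis, "A positive result not confirmed as positive by re-testing at a subsequent visit result will not be considered as an event". Two other sections word the condition differently. Section 3.5.6 asks for a positive titre that "was also confirmed in the next assessment with a titre value of at least 0.6 BU/mL", and section 2.2.2 asks for two consecutive positive central results without mentioning visits. Section 4.12.2 rules out imputation except for partial dates and the primary efficacy endpoint, so a missing inhibitor re-test has no handling of its own. Section 4.11, which lists changes from the protocol, does not mention the visit condition.

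**Protocol.** Section 8.6.1 says "A subject will be considered to have developed an inhibitor if the titer result is ≥ 0.6 BU/mL and verified by repeat testing". Section 8.6 says "A positive inhibitor result (local or central) must be repeated and a duplicate submitted to the central laboratory as soon as possible", and for a suspected inhibitor section 8.6.1 adds "all inhibitor testing must be expedited and a repeat sample obtained as soon as possible to confirm results". Neither ties the repeat to a visit. Section 8.10.4 marks a follow-up period as not applicable. Section 8.10.6 says "No further study-related procedures will be performed after the End of Study Visit, except for follow-up of ongoing AEs"; the sentence goes on to except inhibitor SAEs in Arm 2 as well. Section 9.10 limits that exception to inhibitors already confirmed centrally and gives them 28 days of follow-up.

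**The concern.** A positive that was re-tested and found negative is evidence against an inhibitor. A positive that was never re-tested is missing information. The SAP rule gives both the same favourable score on the primary safety endpoint.

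The place where this can happen is predictable. An inhibitor sample is taken at End of Study in all arms (Protocol 8.10.6.1 and 8.10.6.2), and PTPs leave after at least 100 EDs, so their 100-ED sample may be their last. Inhibitor-negative PUPs leave at 75 EDs. A first positive in that last sample has no planned later sample to confirm it. The Arm 2 exception does not help, because it applies only once confirmation exists.

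**Working it through.** **Is there a plan figure to reproduce?** No. The targets of 200 PTPs and 24 PUPs follow a guideline, and Protocol 11.1 states that no sample size calculation was made. 200 + 24 = 224 is only a sum.

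**Step 1: where does an unresolved positive go?** Protocol 11.3.3.2 builds the denominator from subjects at or above the threshold (100 EDs for PTPs, 50 for PUPs), plus those below it who have an inhibitor (for PUPs, a high-titer inhibitor).

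| Subject with an unresolved positive | Numerator | Denominator |
|---|---|---|
| At or above the threshold | out | in, so counted as inhibitor-free |
| Withdrawn below the threshold | out | out, so excluded |

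Both routes lower the incidence, but only the first counts the subject as inhibitor-free.

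**Step 2: which numerator?** The protocol's numerator has no ED cap. The SAP's landmark incidences count only inhibitors up to 100 EDs for PTPs and, by the same algorithm, up to 50 EDs for PUPs. A first positive at a 75-ED End of Study visit is therefore outside the SAP's 50-ED figure whether or not it is confirmed. It would still belong in the SAP's table of PUPs by EDs at first positive, which has a band above 50 EDs. The figures below use the protocol's uncapped numerator.

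**Step 3: size of one unresolved case.** The interval is Clopper-Pearson (SAP 4.7.1):

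- lower = Beta quantile (0.025; x, n − x + 1)
- upper = Beta quantile (0.975; x + 1, n − x)
- at x = 0 the one-sided 97.5% limit is 1 − 0.025^(1/n), so 1 − 0.025^(1/200) = 1.83% and 1 − 0.025^(1/24) = 14.25%

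| Assumption | SAP rule | Counted as a case |
|---|---|---|
| PTP, ≥ 100 EDs, no other case | 0/200, upper 1.83% | 1/200 = 0.50% (0.01% to 2.75%) |
| PTP, withdrawn < 100 EDs, no other case | 0/200, upper 1.83% | 1/201 = 0.50% (0.01% to 2.74%) |
| PUP, high titer, ≥ 50 EDs, no other case | 0/24, upper 14.25% | 1/24 = 4.17% (0.11% to 21.12%) |
| PUP, high titer, < 50 EDs, no other case | 0/23, upper 14.82% | 1/24 = 4.17% (0.11% to 21.12%) |
| PUP, high titer, ≥ 50 EDs, 4 other cases | 4/24 = 16.67% (4.74% to 37.38%) | 5/24 = 20.83% (7.13% to 42.15%) |

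The numbers of unresolved and other cases are assumptions; the documents give neither.

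**Step 4: how sparse are late PUP samples?** On prophylaxis, visits are 3-monthly from 25 EDs, and a month is 28 days, so the interval is 84 days or 12 weeks. At 2 injections per week (the range in Protocol 3.2.1 is from earlier studies) that is 24 EDs, which puts scheduled samples near 49 and 73 EDs. At 3 per week it is 36 EDs, with one near 61 and the next (97) beyond 75. At every second day it is 42 EDs, with one near 67 and the next (109) beyond 75. The End of Study sample is thus one of only a few after 25 EDs.

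**The case against.** **The protocol obliges a repeat.** Every positive must be repeated as soon as possible, and Protocol 8.10.5 allows unscheduled visits during the study in all arms. The SAP speaks of a subsequent visit, not a scheduled one, so a prompt repeat at an unscheduled visit meets its wording. This stands, and removes most of the apparent conflict with the protocol. What is left is positives whose repeat was not obtained, was not central, or came after End of Study, where the SAP does not say whether it counts.

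**Confirmation is part of the definition.** Repeats are there to rule out laboratory error, and the SAP implements the protocol's own requirement. This stands against calling an unresolved result a true inhibitor. It does not justify reporting it as a refuted one.

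**Withdrawals.** A reader might infer that withdrawn inhibitor cases in general are counted as inhibitor-free. The documents do not support that. Below the threshold such a subject is excluded, and PUPs withdrawn under the Arm 2 high-titer rule have already been confirmed by repeat central testing (Protocol 4.2.1).

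**End of Study positives.** For PTPs, a separate End of Study sample can confirm an earlier 100-ED positive, so a 100-ED sample that is also the last one is a possibility, not the rule. For PUPs, 75 EDs ends the study only if inhibitor-negative, and Protocol 3.3 gives inhibitor-positive PUPs more time. Whether a first, unconfirmed positive at that visit keeps the subject in the study is not stated.

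**PTPs are already reported.** The SAP records the PTP report as completed in November 2019 and, in section 4.1.2, the PTP analysis as complete. This stands, so for PTPs any change is supplementary.

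**Conclusion.** The point holds in a narrow form. SAP 4.7.1 treats missing confirmation as a negative result, and no other section corrects this. The effect runs one way, towards a lower primary safety incidence.

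Per unresolved case, with no other cases assumed, the PTP estimate is 0 instead of 0.50%, and the upper limit is 1.83% instead of 2.75%. For PUPs, only if the titer is high, the estimate is 0 instead of 4.17%, and the upper limit is 14.25% instead of 21.12%. These figures rest on the protocol's uncapped numerator, on target sample sizes, and on subjects at or above the ED threshold.

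The number of such cases cannot be derived from the documents and is probably small, given the duty to repeat. It would go too far to infer that the primary endpoint of every arm is materially biased at its landmark, or that a first positive at 75 EDs would change the SAP's 50-ED PUP incidence.

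**What to change.** In SAP 4.7.1:

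1. Accept any repeat central-laboratory sample as the confirming test, whatever the visit type, including one obtained after End of Study or withdrawal. Use the same wording in 2.2.2 and 3.5.6.
2. Classify each first positive as confirmed, refuted by re-test, or unresolved (no re-test).
3. Keep confirmed cases as the definition for the main analysis, and show the number unresolved beside the estimate.
4. Add a sensitivity analysis that counts unresolved positives as inhibitors in both numerator and denominator, with the same exact interval. For the PUP primary endpoint, restrict it to high-titer results.
5. For PTPs, present this as a post hoc supplementary row and label it so.

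The cost is a few lines of SAP text and one table row. The downside is that the reported incidence may rise slightly.
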